**Sample Shipment**

All specimens should be correctly labeled with patient initials, study-specific subject ID number, protocol number, and date and time of collection. NOTE: In the event that baseline specimens are available but the patient is not successfully registered to the protocol, do not submit the patient's specimens. Overnight shipments should occur on Monday through Wednesday except when the following day is a holiday. A fax or call should be placed to the Analytical Pharmacology Core Laboratory prior to shipment providing the shipment tracking information.

**7.3 Non invasive imaging studies**

Non invasive imaging studies assessing changes in tumor metabolism will be performed both at RPCI and JHU. This study will evaluate changes in tumor metabolism in all patients undergoing PET/CT utilizing FDG. Patients will have PET/CT studies before starting entinostat administration and during week 5.

**7.4 Optional tumor Samples**

All Patients with accessible tumors will be asked to undergo an optional tumor biopsy within 21 days before starting treatment and on Day 30 of Cycle 1 +/- 2 days. This tumor biopsy is not required for patients to take part in this protocol.

### 7.4.1. Formalin-Fixed Paraffin-Embedded Tissue

#### Sample Collection Time Points

*Samples may be obtained from any time prior to drug dosing.*

Sample	Screening Visit
Original diagnostic material	X
Any subsequent biopsy material prior to dosing	X

#### Sample Collection Procedure

Per institutional procedures, obtain a whole formalin-fixed paraffin block for patient. Paraffin blocks should contain a tumor specimen measuring at least 0.5 cm x 0.5 cm x 100 microns. Paraffin blocks may be from original diagnosis or optional biopsy any time prior to first drug treatment.

#### Packaging of Paraffin Block

- Place the paraffin block in a specimen container.

#### Shipment of Paraffin-embedded Tissue

**Notification of sample shipment should be sent by email to**

**[name] and [name] at [[contact]](mailto:[contact]) and [[contact]](mailto:[contact]).**

#### Analysis

These samples will be analyzed for microvessel density (anti-CD34 staining), HIF-1  $\alpha$  staining, acetylated Histone and CD4+/FOXP3+ T cells. All IHC studies will be done with established protocols in [name] lab.

### 7.4.2 Optional fresh tumor samples

#### Sample Collection

- Optional tumor biopsy samples will be collected from patients with accessible tumor per institutional procedure.

- The specific biopsy samples and time points for collection of fresh tumor samples are given below:

Time Points	Number of Tumor Biopsy Samples per Time Point
Pretreatment	1
On treatment *	1

\* The on-treatment samples will be collected 2 hours following the most recent dose of entinostat on Day 30 Cycle 1 +/- 2 days. To ensure that these samples are obtained at the correct time, patients are urged to take their entinostat dose in the clinic on the day of on-treatment sample collection. The time of the entinostat dose and sample collection must be recorded.

Attn: [name]

Laboratory of [name]  
Division of Hematology and Oncology,  
Department of Medicine,  
Indiana University School of Medicine  
[name]  
[name]  
Indianapolis, IN 46202

Notification of sample shipment should be sent by email to  
[name] and [name] at [[contact]](mailto:[contact]) and [[contact]](mailto:[contact]).

These samples will be also analyzed for microvessel density (anti-CD34 staining), HIF-1  $\alpha$  staining, acetylated histone, CD4+, CD4+/FOXP3+, and CD8+ T cells. All IHC studies will be done with established protocols in [name] lab.

**8. STUDY CALENDAR**

**Pre-study evaluations are to be performed within 4 weeks prior to start of therapy.**

Treatments and Evaluations	Pre-Study	Cycle 1 and subsequent cycles																				Every 4 weeks between cycles 	End of Treatment 	Follow-Up 9a			
		Week -2						Week 1							Week 3												
		D	D	D	D	D	D	D	D	D	D	D	D	D	D	D	D	D	D	D	D						
		-14	-13	-12	-11	-10	-9	-7	1	2	3	4	5	6	7	15	16	17	18	19	20				21		
Entinostat dosing		√							√								√										
IL-2 dosing									√	√	√	√	√			√ 	√	√	√	√							
Informed Consent	√																										
History and Physical	√								√							√								√ 8a	√		
Vital Signs and Weight	√	√ 					√	√	√							√								√ 8a	√		
ECOG Performance Status	√	√ 						√	√							√								√ 8a	√		
CBC w/diff., plts	√	√ 						√	√							√								√	√		
Urine analysis, (CMP) 	√							√	√							√								√	√		
PT/PTT/INR	√							√	√							√								√	√		
Serum Pregnancy test 	√																										
Head MRI or CT	√																										
EKG,MUGA, cardiac stress test 	√																										
PFT	√																										
Tumor Measurements 	√																							√ 	√		
Pharmacodynamic Samples 5 & 5a		√ 					√	√	√							√									√		
Serum for microRNA 		√						√	√							√											
Tumor Needle Biospy 	√																										
PET/CT 	√																										
Concomitant Meds	√	√ 																						√	√		
Survival follow-up																										√	

1. Comprehensive metabolic panel (CMP) to include measurement of sodium potassium, chloride, bicarbonate/CO, BUN, creatinine, glucose, total bilirubin, corrected calcium (CC= Serum calcium+0.8(4-Serum albumin)), total proteins, albumin, AST, ALT, alkaline phosphatase, LDH, magnesium, and phosphate.
2. Pregnancy test required within 14 days of starting study drug for women of child bearing potential only.
3. Patients who are over 40 or have had previous myocardial infarction greater than 6 months prior to entry will be required to have a negative or low probability cardiac stress test for cardiac ischemia, as well as EKG and MUGA. Subsequent cardiac tests may be performed at the discretion of the Principal Investigator as clinically indicated.
4. Include CT scan, bone scan, MRI or ultrasound (additional tests may be performed as clinically indicated) Perform on week 11 of each cycle (+/- 7days) and every 8-12 weeks (+/- 2 weeks) on entinostat. Bone scan is required at baseline for patients with bone pain or evidence of bone lesions on CT scan.
5. Obtain pre-dose on day -14; day -7; pre-dose day 1 and at 8 hrs and 24 hrs post dose of entinostat; and pre-dose day 15 during the first cycle and at the time of progression.
  - 5a. Obtain PD sample on cycle 2 pre-dose day 1 and day 15 pre-dose; Repeat for cycle 3 pre-dose day 1 and day 15 pre-dose.
6. Optional Core biopsy and fine needle aspirate obtained within 21 days prior to start of cycle 1 and on day 30 of cycle 1 +/- 2 days.
7. To be performed prior to cycle 1 and on week 5 to assess changes in tumor blood metabolism.
- 8.** Maintenance Period, Local labs results acceptable.
  - 8a. May be performed every 8 – 12 weeks between cycles.
9. Performed 30 days (+/- 4 days) following last dose of study drug.
  - 9a. every three months afterward assessment may be obtained via telephone.
10. Beginning of course 2 (day 15) may be delayed up to 7 days.
11. Must be performed within 3 days prior to day -14.
12. Obtain Serum for microRNA for cycles 2 and 3 on day 1 pre-dose and at time of progression

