#### **4.1 Entinostat / aldesleukin administration and definition of Dose-Limiting Toxicity (DLT)**

Patients with metastatic renal cell carcinoma and no prior therapies will be eligible for treatment. One cycle of treatment (84 days) will consist of 2 courses of high dose aldesleukin 600,000 units/kg administered IV every 8 hrs. on day 1-5 and day 15-19 ( $\pm$  7 days) (maximum 28 doses), and entinostat orally (1-2 hrs. prior to aldesleukin infusion) given every 2 weeks starting on day-14, continuously. Entinostat is to be taken on an empty stomach, at least 1 hour before or 2 hours after a meal. Tumor response assessment will be performed on week 11 ( $\pm$  7 days). In the event of clinical benefit (stable disease or tumor shrinkage) patients will receive a second cycle of therapy.

Entinostat will continue every 2 weeks ( $\pm$  7 days dependent on adjustments necessary for aldesleukin dosing) until documented disease progression or 8 weeks following documented complete response. Patients with evidence of tumor shrinkage may receive up to 3 cycles of high dose aldesleukin therapy. Cycle 2 will start on or within 2 weeks following day 85 (or last day of cycle dependent on dosing adjustment) as in cycle 1. Cycle 3 can start within 2 weeks after completion of cycle 2. Patients with stable disease by RECIST V.1.0 criteria, but without evidence of tumor shrinkage after two cycles will receive only entinostat until disease progression is documented.

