#### 4.3 Duration of Follow Up

Follow up safety evaluations will occur 30 days (+/- 4 days) after last dose of study drug or until resolution of any drug related toxicity (telephone contact is acceptable). Follow up will include review of concomitant medications and adverse events.

Patients (both Phase I and Phase II) will be followed up after completion of therapy every three months for survival assessment (telephone contact is acceptable) or until completion of primary endpoint/ termination of study.

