## 5.6 Toxicity Criteria for Discontinuing Treatment

Patients will not be considered for further therapy if the following toxicities are encountered:

- 5.6.1 Pulmonary toxicity requiring endotracheal intubation
- 5.6.2 Renal dysfunction requiring dialysis
- 5.6.3 Grade 4 cardiac dysrhythmia or Grade 2 or 3 dysrhythmia not easily controlled with medical management
- 5.6.4 Myocardial ischemia (Grade 3 or 4) or infarction or symptomatic myocarditis (note: asymptomatic CPK or CPK-MB band elevations without EKG changes are not a contraindication to further treatment).
- 5.6.5 Coma
- 5.6.6 Life-threatening sepsis
- 5.6.7 Pericardial tamponade
- 5.6.8 Bowel ischemia or perforation
- 5.6.9 Grade 4 hypertension or hemorrhage, symptomatic grade 4 venous thromboembolic event, nephritic syndrome
- 5.6.10 Any grade arterial thromboembolic event
- 5.6.11 Inability of subject to comply with study requirements
- 5.6.12 Any other severe or life-threatening toxicity which, in the opinion of the investigator, would preclude further treatment with these agents, or has not resolved to baseline 8 weeks after treatment.

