## 9. MEASUREMENT OF EFFECT

Patients will undergo CT scans at week 11 (+/- 7 days) of each cycle during aldesleukin administration and then every 8-12 weeks (+/- 2 weeks).

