### 9.2.3 Evaluation of best overall response

The best overall response is the best response recorded from the start of the treatment until disease progression/recurrence (taking as reference for PD the smallest measurements recorded since the treatment started). In general, the patient's best response assignment will depend on the achievement of both measurement and confirmation criteria.

Target lesions	Non-Target lesions	New Lesions	Overall response
CR	CR	No	CR
CR	Incomplete response/SD	No	PR
PR	Non-PD	No	PR
SD	Non-PD	No	SD

PD	Any	Yes or No	PD
Any	PD	Yes or No	PD
Any	Any	Yes	PD

- Patients with a global deterioration of health status requiring discontinuation of treatment without objective evidence of disease progression at that time should be classified as having “symptomatic deterioration”. Every effort should be made to document the objective progression even after discontinuation of treatment.
- In some circumstances it may be difficult to distinguish residual disease from normal tissue. When the evaluation of complete response depends on this determination, it is recommended that the residual lesion be investigated (fine needle aspirate/biopsy) to confirm the complete response status.

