#### 9.2.4 Confirmation

- The main goal of confirmation of objective response is to avoid overestimating the response rate observed. In cases where confirmation of response is not feasible, it should be made clear when reporting the outcome of such studies that the responses are not confirmed.
- To be assigned a status of PR or CR, changes in tumor measurements must be confirmed by repeat assessments that should be performed no less than 4 weeks after the criteria for response are first met. Longer intervals as determined by the study protocol may also be appropriate.
- In the case of SD, follow-up measurements must have met the SD criteria at least once after study entry at a minimum interval (in general, not less than 6-8 weeks) that is defined in the study protocol

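### Section 9 and the study calendar disagree on whether CTs continue in patients who stop both drugs without progression; on the calendar, nothing after the end-of-treatment scan would date their progression

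*Combined protocol and SAP*

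**What the plan says.** Section 9 schedules CT at week 11 "of each cycle during aldesleukin administration and then every 8-12 weeks". It names no end and does not make the later scans depend on being on drug.

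Note 4 of the Study Calendar (Section 8) reads: "Perform on week 11 of each cycle (+/- 7days) and every 8-12 weeks (+/- 2 weeks) on entinostat". The calendar ticks tumor measurements at the End of Treatment visit, which note 9 places 30 days (± 4) after the last dose. The Follow-Up column holds survival follow-up only. Section 4.3 agrees: patients are "followed up after completion of therapy every three months for survival assessment (telephone contact is acceptable").

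Two routes lead off both drugs without progression. Section 4.1 continues entinostat "until documented disease progression or 8 weeks following documented complete response". Section 5.6 gives a list of severe toxicities under the rule "Patients will not be considered for further therapy if the following toxicities are encountered".

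The endpoints look beyond the last dose. Section 9.2.3 says "The best overall response is the best response recorded from the start of the treatment until disease progression/recurrence". Section 9.2.4 says that a partial or complete response "must be confirmed by repeat assessments that should be performed no less than 4 weeks after the criteria for response are first met". Section 9.2.5 runs duration of response to objectively documented recurrence or progression. PFS and time to progression are secondary endpoints in Section 11.3, which gives no censoring rule for them.

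**The concern.** A site that follows Section 9 would go on scanning a complete responder after entinostat stops. A site that follows note 4 and Section 4.3 would make one more scan and then telephone every three months. Both could say that they followed the protocol, and their progression data would not be comparable.

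On the calendar reading, a progression after the end-of-treatment scan has no scheduled assessment to date it; only death is still captured. This affects PFS, time to progression and duration of response. The primary endpoint is exposed in one place: a patient who stops early for toxicity, and whose first response is seen at the end-of-treatment scan, has no clearly scheduled confirming scan. Section 11.7.3 keeps that patient in the denominator, and Section 9.2.7 counts unassessable patients as failures.

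**Working it through.** **1. The texts side by side**

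| Place | Week-11 scan | Later scans | After end of treatment |
|---|---|---|---|
| 4.1 | yes, no on-drug condition | not stated | not stated |
| Section 9 | yes, each aldesleukin cycle | every 8-12 weeks, no end | can be read as continuing |
| Calendar, note 4 | yes, each cycle | every 8-12 weeks while on entinostat | none |
| Calendar columns | – | between cycles | one scan at 30 ± 4 days, then survival only |
| 4.3 | – | – | survival contact, telephone allowed |

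The column positions are taken from extracted text. The last tumor-measurement tick sits one column before the survival tick, in line with the other End of Treatment items.

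**2. Timing for early toxicity stops**

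- Suppose the last dose falls within the aldesleukin courses, about day 3 to day 26 (course 2 ends on day 19; plus the permitted 7-day delay = 26).
- End-of-treatment scan: day 3 + 30 = 33 to day 26 + 30 = 56.
- Week 11 is days 71-77; with ± 7 days the window is days 64-84.
- Earliest confirming scan: day 33 + 28 = 61 to day 56 + 28 = 84.

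So the end-of-treatment scan comes before the week-11 window. If the week-11 scan is kept, it can usually serve as the confirming scan.

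**3. Timing for complete responders**

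Take a complete response first seen at about day 74 of cycle 1.

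- Counting 8 weeks from that scan: 74 + 56 = day 130, last entinostat dose about day 127, end-of-treatment scan about day 157. The cycle-2 week-11 scan falls at 84 + 74 = day 158.
- If the response counts as documented only when confirmed at day 158: 158 + 56 = day 214, last dose about day 211, end-of-treatment scan about day 241.
- If cycle 3 is given, its week-11 scan falls at 168 + 74 = day 242.

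The last calendar scan is therefore at about day 158 to day 242, with survival contact only after that. A complete response first seen later moves these dates back.

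**4. How many patients**

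Section 2.2 reports 8 complete responses in 95 patients on high dose aldesleukin. 36 × 8/95 = 3.03. The exact 95% interval for 8/95 is 3.7% to 15.9%, or 1.3 to 5.7 of 36. The documents do not give the number of toxicity stops.

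**5. Primary endpoint**

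Section 11.3 declares activity at 11 or more responses in 36. The exact binomial gives P(X ≥ 11) = 0.089 at a 20% response rate and 0.910 at 40%, which reproduces the stated errors of 0.09 and 0.09. As a worst case, let k patients be impossible to score as responders, so that n = 36 − k can respond:

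| k (assumed) | P(X ≥ 11) at 40% | P(X ≥ 11) at 20% |
|---|---|---|
| 0 | 0.910 | 0.089 |
| 1 | 0.888 | 0.075 |
| 2 | 0.862 | 0.062 |
| 3 | 0.831 | 0.051 |
| 4 | 0.795 | 0.041 |

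A fixed schedule would not recover all of that loss. Assume that the k patients have a 20% chance of response and the others 40%. The recoverable power is then 0.011, 0.025, 0.043 and 0.064 for k = 1 to 4 if the early scan scores none of them, and 0.005, 0.012, 0.020 and 0.030 if it captures half. Type I error only falls.

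**6. Time-to-event endpoints**

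Section 11.3 estimates the failure rate as events divided by summed exposure time. If an off-drug patient is censored at the last scan, later progression-free time is lost and the rate is too high. If the patient is counted progression-free to the last telephone contact, unseen progressions make the rate too low. Without a censoring rule, the plan does not say which.

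**The case against.** **The week-11 scan may already be secure.** In note 4 the on-drug condition follows the 8-12-weekly clause, not the week-11 clause. Section 4.1 states the week-11 assessment without condition, and Section 9.2.7 wants every included patient assessed for response even after major treatment deviations. On that reading early stoppers keep the scan, and step 2 shows that it usually confirms a first response. Section 5 also stops aldesleukin alone for severe reactions to it, so some of these patients could stay on entinostat and be scanned. This stands, and it removes most of the primary-endpoint effect.

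**The plan already softens the gap.** Section 9.2.3 asks that progression be documented even after treatment stops. Note 4 allows extra tests when clinically indicated. Section 9.2.4 provides for reporting unconfirmed responses: "In cases where confirmation of response is not feasible". These are partial mitigations. The Section 9.2.3 request sits in the bullet on symptomatic deterioration and sets no schedule, and none of the three requires a scan.

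**A reader might infer that the scan gap could decide the PFS comparison.** Suppose 33 patients progress at 2.77 per person-year (33/2.77 = 11.91 person-years) and 3 complete responders do not progress. Their last calendar scan is 0.47 to 0.70 years from first dose, which gives 33/(11.91 + 3t) = 2.48 to 2.35. Scans showing them progression-free for 2 or 3 years give 1.84 or 1.58. The documents do not support this. The 2.77 is ln 2/0.25 = 2.77, the whole historical arm's 3-month median turned into a rate, and that arm already contains its 8 complete responders, so they enter twice. Keep the overall median at 3 months with 3/36 never progressing: the other 33 then progress at ln(2.2)/0.25 = 3.15 per person-year, or 10.46 person-years. The calendar gives 2.78 to 2.63, and 2 or 3 years of scans give 2.00 or 1.70, with no true benefit at all. The swing reflects setting an exponential benchmark against a long tail of progression-free patients, not harm from the calendar. Section 11.3 also plans only 12 months of follow-up after accrual, so late enrollees could not reach 2 or 3 years.

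**Conclusion.** The inconsistency is in the text and worth correcting as a cheap improvement. On the calendar reading, patients who stop both drugs without progression have no scheduled scan after the end-of-treatment visit to date later progression, and an early stopper's response may go unconfirmed.

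About 3 of 36 patients would be affected as complete responders (1.3 to 5.7, if the historical 8/95 applies), plus an unknown number of toxicity stops. For the primary response rate the effect is small and conservative: recoverable power of about 0.005 to 0.06 under the assumed 1 to 4 affected patients, and largely nil if the week-11 scan is kept. A reader might infer a risk of a false claim of activity; there is none, because type I error falls. For PFS and time to progression the direction depends on the censoring choice, and the documents do not support a figure for its size.

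**What to change.** In note 4 of the calendar, Section 9 and Section 4.3, use the same rule for a patient who stops both drugs without progression, whether for toxicity or after complete response:

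- keep the week-11 scan;
- make a confirmatory scan at least 4 weeks after a first partial or complete response;
- continue CTs every 8-12 weeks until progression, new anticancer therapy, death, withdrawal of consent or study termination.

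The cost is wording in three places and a few routine CTs, of a kind already planned, in a handful of patients. The change dates progression for these patients. It does not cure the mismatch between a median-derived benchmark and a long progression-free tail, so a failure rate below 2.77 would still need cautious reading.

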## 9. MEASUREMENT OF EFFECT

Patients will undergo CT scans at week 11 (+/- 7 days) of each cycle during aldesleukin administration and then every 8-12 weeks (+/- 2 weeks).

### **Response Evaluation Criteria in Solid Tumors (RECIST V.1.0) Quick Reference**

Only patients with measurable disease at baseline should be included in protocols where objective tumor response is the primary endpoint.

**Measurable disease** - the presence of at least one measurable lesion. If the measurable disease is restricted to a solitary lesion, its neoplastic nature should be confirmed by cytology/histology.

**Measurable lesions** - lesions that can be accurately measured in at least one dimension with longest diameter  $\geq 20$  mm using conventional techniques or  $\geq 10$  mm with spiral CT scan.

**Non-measurable lesions** - all other lesions, including small lesions (longest diameter  $< 20$  mm with conventional techniques or  $< 10$  mm with spiral CT scan), i.e., bone lesions, leptomeningeal disease, ascites, pleural/pericardial effusion, inflammatory breast disease, lymphangitis cutis/pulmonis, cystic lesions, and also abdominal masses that are not confirmed and followed by imaging techniques; and.

- All measurements should be taken and recorded in metric notation, using a ruler or calipers. All baseline evaluations should be performed as closely as possible to the beginning of treatment and never more than 4 weeks before the beginning of the treatment.
- The same method of assessment and the same technique should be used to characterize each identified and reported lesion at baseline and during follow-up.
- Clinical lesions will only be considered measurable when they are superficial (e.g., skin nodules and palpable lymph nodes). For the case of skin lesions, documentation by color photography, including a ruler to estimate the size of the lesion, is recommended.

